1.1 Title, Registration, versions, and revisions

Title: Reducing Late-Life Anxiety and Improving Function with Self-Directed Relaxation

IRB: 32239 (last approved date: 03/17/2017)

Clinicaltrials.gov number: NCT02429778

Funding: Brain and Behavior Research Foundation

2 Contact: [name] (Principal Investigator)

Email: [contact]

3 Background

3.1 Behavioral, non-pharmacological treatments for anxiety have been effective in treating late-life anxiety and avoidance. In a meta-analysis of late-life anxiety psychotherapies, Thorp and colleagues (2009) found that Progressive Muscle Relaxation (PMR) resulted in the largest reductions in anxiety compared with waitlist controls, supportive therapy, and other efficacious therapies such as cognitive behavioral therapy (CBT). PMR is a component of CBT for anxiety, yet only one session of CBT is typically devoted to teaching PMR, which may be inadequate for older individuals to fully learn the skill. As such, older adults may not consolidate the techniques for utilizing PMR despite its potential to significantly reduce anxiety. Despite evidence in support of PMR for late-life anxiety (Thorp et al., 2009) and reduction of somatic symptom (e.g., Gift, Moore & Soeken, 1992), this intervention is not widely available to older adults. [name] began to address this issue by developing a self-directed version of PMR: Breathing, Relaxation, and Education for Anxiety Treatment in the Home Environment (BREATHE).

4 Study Summary and Aims

4.1 Purpose: The PI developed a self-directed program to treat late-life anxiety called Breathing, Relaxation, and Education for Anxiety Treatment in the Home Environment (BREATHE). This program consists of weekly video lessons that participants watch on DVD along with weekly telephone check-ins. In BREATHE participants will learn two behavioral interventions: diaphragmatic breathing and progressive muscle relaxation (PMR). The purpose of the study is to examine whether the self-directed BREATHE program is superior to a wait list control in reducing anxiety in older adults with anxiety disorders.

5 Inclusion and Exclusion Criteria

5.1 Inclusion Criteria: Men or women aged 60 and older who meet DSM-5 criteria for an anxiety disorder(s) (Generalized Anxiety Disorder, Panic Disorder, Agoraphobia, Social Anxiety Disorder or Anxiety Unspecified Anxiety Disorder or Anxiety Disorder Other Specified). Participants must understand English well-enough to participate in treatment.

5.2 Exclusion Criteria: Comorbid psychiatric disorders are acceptable unless participant has Obsessive Compulsive Disorder, psychotic disorders or serious mental illness (bipolar disorder). Participants must not be taking benzodiazepines more than once a week. Participants with dementia or cognitive impairment, defined as a score of 6 or greater on the Short Blessed Test

will be excluded. Participants enrolled in other psychological or pharmacological treatment studies for psychiatric conditions will be excluded.

6 Study Endpoints: Assessments will occur at baseline, 4 weeks and 8 weeks.

7 Study Procedures

7.1 Screening Procedures: A telephone interview will be conducted with potential participants to determine study eligibility. Potential participants will be offered the opportunity to complete this interview as a face-to-face interview if the participant would prefer to do so. During the interview, study staff will explain the study, its requirements and answer any questions that the potential participant has. Upon the potential participant's willingness to be screened, study staff will determine whether patients meet age criteria (60+) and cognition exclusion criteria based on performance on the Short Blessed Test (SBT). The SBT (Katzman et al., 1983) is a weighted 6-item brief cognitive assessment that can be administered in person or over the phone. This measure, also called the Blessed Orientation-Memory-Concentration Test, and scores of 0 to 5 indicate normal cognition and scores ≥ 6 suggest the presence of cognitive impairment. The SBT is administered to assess for cognitive impairment, an exclusion criterion. The SBT evaluates the following cognitive domains: orientation, registration, attention, and memory recall. It has acceptable test-retest reliability, convergent validity with other cognitive measures, and high specificity and adequate sensitivity for the detection of dementia (Milne et al., 2008). Any participants who do not pass the SBT (≥ 6) will be excluded from the study at that time. Participants excluded due to cognitive scores will be provided the feedback that their performance may suggest the presence of cognitive problems, but further assessment is needed. Referrals will be provided to them at that time.

An additional screening question about whether individuals take any benzodiazepines will be included in the telephone screen to assess this exclusion criteria. Participants will be excluded if they use short-acting benzodiazepines (lorazepam, alprazolam) twice a day or more frequently. Participants will be excluded if they use long-acting benzodiazepines (flurazepam, librium, clonazepam, diazepam, temazepam) once a day or more frequently.

7.2 Baseline Visit: Participants who are deemed to meet inclusion/exclusion criteria for age, cognition, and benzodiazepine use will be invited to an approximately two to three hour face-to-face baseline assessment and paid \$30. During the initial face-to- face assessment informed consent will be obtained and the baseline assessment visit will be completed. Those who are deemed not eligible for the treatment will be provided with appropriate referrals. The remaining assessment of inclusion/exclusion criteria will take place during the baseline assessment. Participants must meet DSM-5 criteria for an anxiety disorder(s) Generalized Anxiety Disorder, Panic Disorder, Agoraphobia, Social Anxiety Disorder or unspecified anxiety disorder. Those patients with Obsessive Compulsive Disorder (OCD) will be excluded as efficacious treatments for OCD are well established (e.g., exposure and response prevention). Assessment of anxiety disorders will be completed by trained study staff who use the Structured Clinical Interview for DSM-5 Disorders (SCID-5). At the beginning of the face-to-face baseline assessment, written informed consent and consent for audiotaping of the SCID-5 will be obtained. Audiotaping will

be used for supervision purposes and to assess inter-rater reliability of diagnoses. Participants will be allowed to continue with the study if they do not consent to audiotaping of the SCID-5 interview.

Participants with comorbid psychiatric disorders, such as depression or post-traumatic stress disorder, will be included. However, participants with documented diagnosis of dementia or a serious psychiatric disorder (psychotic disorder, schizophrenia, schizoaffective disorder, or bipolar disorder) or identification of serious psychiatric disorders by SCID-5 screening questions will be excluded. Additional baseline assessments include completion of a demographic questionnaire, administration of the Geriatric Anxiety Scale (GAS) to assess anxiety symptom severity, Activity Card Sort (ACS) to assess activity engagement, Somatic Symptom Scale – (SSS-8), Older Adult Social Evaluative Situations Scale (OASES), and depression symptoms measured with the Patient's Health Questionnaire (PHQ-9). Comorbidity will be measured with the Deyo-adjusted Charlson Comorbidity Index (CCI). This is calculated from the self-report comorbidity questionnaire in the demographic questionnaire.

Participants who do not meet SCID-5 criteria will be paid \$30 and excluded from the study after completing the self-report measures and the ACS. Additional participants will be recruited to meet the goal of 40 participants randomized.

7.3 Measures:

In the baseline demographic questionnaire, basic participant characteristics including gender, marital status, race, and ethnicity will be collected. Additional questions about participants' previous experience with relaxation, breathing training, meditation, Tai chi, and any other similar techniques will be assessed. The information needed about medical conditions to complete the Deyo-adjusted Charlson Comorbidity Index will come from the comorbidity questions (Katz et al., 1996) about medication conditions on the demographic questionnaire.

The Structured Clinical Interview for DSM-5 Disorders is a structured interview that assess diagnostic criteria each DSM-5 disorder. The interview can take 90 to 120 minutes. The SCID-5 is included to assess inclusion and exclusion criteria.

Geriatric Anxiety Scale (GAS). The GAS is a 30-item measure of somatic, cognitive, and affective symptoms of anxiety. The first 25 items of the measure are used to compute the total score; the last 5 items provide information about the content of worries or fears. Participants provide severity ratings for items using on a four-point Likert-type scale. The GAS is administered to assess severity of anxiety symptoms and is the primary outcome in this study.

Patient Health Questionnaire-9 (PHQ-9). The PHQ-9 is a 9-item depression assessment rated on a four-point Likert-type scale with scores ranging from 0 to 27. It includes one item that inquires about suicide ideation. The PHQ-9 is administered to characterize participants' depression symptoms.

Somatic Symptom Scale (SSS-8). The SSS-8 is an 8-item somatic symptom assessment rated on a

five-point Likert-type scale with scores ranging from 0 to 32. The SSS-8 is administered to characterize participants' somatic symptoms.

Older Adult Social Evaluative Situations Scale (OASES). This measure is a 37-item measure that assess anxiety about and avoidance of social situations. This is included as a secondary outcome measure.

Activity Card Sort (ACS). The ACS contains 80 photographs that depict the performance of instrumental activities, low-physical-demand leisure activities, high-physical-demand leisure activities, and social activities. The ACS was selected as a measure of activity engagement for the present study because it assesses the presence and the loss of activity. We will administer the ACS using an interactive sorting task (Q-sort procedure; Albert et al., 2009). Participants will be asked to divide the stack of photographs into a pile of activities that they currently do not perform and activities that they do perform. Then, participants will divide the stack of activities that are currently not performed into two additional piles: "never-performed" and "used-to-but-no-longer-perform" activities. For the stack of activities that are currently performed, these will be divided into "hard-to-do" and "easy-to-do" activities based on a time frame of "today or the past 30 days."

The four piles will be used to calculate lifestyle-adjusted function (Albert et al., 2009). By excluding activities that participants never performed, the lifestyle-adjusted function score will accurately reflect loss, gain, or changes in activity participation. We also have participants select their top five activities that they would like to do more frequently if not experiencing anxiety. Participants will make ratings of these measures before and after treatment.

Physiological measures are systolic and diastolic blood pressure, pulse rate, and oxygen saturation measured with a Welch Allyn Spot Vital Signs monitor. Five-minute resting baseline assessments will be obtained at baseline and post-treatment. A five-minute post-relaxation practice will also be obtained at post-treatment.

7.4 Randomization: Participants will be randomized to BREATHE or wait list. A statistician will advise on completing randomization in order to obtain two equal groups. Randomization scheme will be created by individuals not related to the study. At the baseline visit, [name] or her research assistant will open a sealed envelope that contains the results of the randomization. Participants will not be told which group they are randomized to, but based on the differences in the active intervention compared with wait list; they will likely be able to ascertain what their randomization group is. Because of the nature of psychological interventions, it is difficult to achieve blindness in RCTs with psychological interventions.

7.5 Study Design

The objectives will be addressed with an 8-week randomized control trial (RCT) that compares a 4 week treatment, BREATHE (described below), and 4 weeks of practice of the intervention, progressive muscle relaxation, with a wait list control. Wait-list

participants will be offered the option to enroll in the active treatment after the 8 week post-treatment assessment.

7.5.1 Protocol for BREATHE Intervention Group:

Baseline Assessment/Pre-treatment Assessment Protocol: After the baseline assessment is complete, participants will be instructed on how to complete Subjective Units of Distress Scale (SUDS) before and after each PMR practice throughout the study. SUDS ratings ranging from 0 to 100 (least to most distressed) have been used to document a patient's subjective experience during anxiety disorder treatments such as systematic desensitization and trauma- focused therapies. This measure was selected to track anxiety (0 = no anxiety, 100 = extreme anxiety) before and after practicing PMR. This is an important part of the clinical intervention in that it draws the patient's attention to the changes in anxiety following the PMR intervention. SUDS may help monitor homework compliance and identify problems, such as relaxation-induced anxiety.

Instructions on how to use and play the DVD will be provided. Portable personal DVD players will be lent to participants who either do not have access to a DVD player or would prefer to use a portable player. The surface of the DVD player will be cleaned with rubbing alcohol wipes to disinfect the players between participants. Participants will be provided their own copy of the BREATHE DVD to use throughout treatment and keep for future use.

BREATHE Intervention Overview: BREATHE is a four week behavioral intervention that uses evidence- based behavioral techniques (diaphragmatic breathing and progressive muscle relaxation) to reduce anxiety symptoms and avoidance in older adults. BREATHE is designed to be aligned with the tenets of Social Learning Theory (Bandura, 1971). BREATHE will incorporate experiential and observational learning to promote decreased avoidance of identified activities. In Social Learning Theory, Bandura posits that learning can take place through observation of a model's behavior in addition to the observer's direct experience. Thus, decreasing reliance on avoidance as a coping strategy among those with anxiety disorders can be accomplished through: (1) the reduction of anxiety symptoms through experiential learning of relaxation and breathing skills, (2) experiential learning through approaching situations that are uncomfortable and avoided after using PMR, and (3) observation of a model who engages in an anxiety- evoking situation avoided by the observer. eHealth interventions for young adults use vignettes and case examples to model how to apply newly learned skills to overcome common life obstacles, such as work stress. BREATHE videos will use this format and will incorporate age- appropriate examples such as anxiety about engaging in exercise, health-promoting activities, financial worries, and worries about one's own health and health of family members rather than vignettes about work, school, and interpersonal concerns that are less relevant to older adults (e.g., Gould & Edelstein, 2010). The combination of experiential and observational learning will help participants apply the skills learned in treatment to situations encountered in daily life. Vignettes will be used to model these behaviors aligned with Social Learning Theory.

The innovative aspect of this treatment is that BREATHE will be delivered via video lessons recorded on DVDs. The script for the DVD treatment is included as an attachment. Participants can view the DVD on a personal DVD player. The treatment also involves telephone check-ins during weeks one through four. The treatment will be delivered via DVD. The following four chapters detail the skills that make up the program. Each session will be turned into video lesson approximately 20-40 minutes in duration. During weeks 1-4 participants will view a new video module each week. Practice exercises are assigned each week and separate videos will be filmed to guide participants during practice. Homework forms are included for patients to use to record their practices. Participants will be asked to practice PMR twice daily as part of the behavioral treatment.

Participants will receive a telephone call from study staff on a weekly basis to check in about problems with the videos or the intervention. Study staff will contact participants each week to troubleshoot and answer questions. Homework compliance will be reported by phone to study staff. Participants will be asked to report the number of times they practiced PMR and their SUDS ratings before and after the PMR practice during weekly telephone check ins. Each weekly session will consist of brief psychoeducation, teaching of new skills, and assigned home practice. The content of the weekly sessions is available from the PI or is described in the published outcome paper.

7.6 Week 4 Assessment: At the end of the BREATHE treatment (week 4), participants will be asked to complete the GAS over the telephone. Participants will also be instructed to continue with home practice of PMR for four weeks. One additional reminder post card and telephone call at week 6 will occur to help patients with any issues that arise. After a month of home practice, which is 8 weeks from baseline assessment, participants will come to the VA for a face-to-face post-treatment assessment with study staff and will be paid \$30.

7.7 Post-treatment Assessment/8 weeks: At post-treatment, a 5 minute baseline measurement of heart rate, blood pressure, and pulse will be obtained. Then, the 16-muscle group PMR will be practiced by the BREATHE and the control group by briefly viewing the initial PMR instructions video (control only) and then following along. BREATHE participants will be shown the 16 muscle group practice video to follow along with. Following this practice, a 5-min physiological measurement period will be obtained to examine physiological variables as a function of participant's experience with PMR. The Anxiety disorder sections of the SCID-5 will be administered at post treatment to determine if participants meet criteria for any anxiety disorders. Then, the participants will complete the GAS to assess anxiety symptom severity, SSS-8 to assess somatic symptoms, PHQ-9 to measure depressive symptoms, OASES to assess anxiety about and avoidance of social situations, and ACS to assess activity engagement. We will attempt to obtain partial follow-up data from lost to follow-up participants, through mailed questionnaires (GAS and PHQ-9) in participants who do not complete the final face-to-face assessment. We will solicit feedback from participants on their experience with BREATHE to determine what participants liked, what issues arose, and

what participants did not like about the treatment or DVDs (see attached post-treatment questionnaire).

8 Statistical analyses

- 8.1 Baseline analyses: We compared baseline group means and distributions using χ^2 and independent samples t-tests to determine whether randomization resulted in equivalent groups.
- 8.2 Dropouts: We examined whether participants completing the study differed from those who did not complete the study (i.e., drop-outs). Efforts were made to obtain data from individuals who discontinued participation.
- 8.3 BREATHE Intervention: Engagement with the BREATHE intervention was examined by estimating the intervention dose via a calculation of relaxation practices completed during the four-week intervention phase. The activities that participants engaged in using breathing or PMR skills were summarized.
- 8.4 Outcome analyses: Mixed effects models were used to examine the primary and secondary hypotheses using intent-to-treat principles. Maximum likelihood estimation for missing values was used in the mixed effects models. In all models, the fixed factor was treatment type (BREATHE vs. wait list), with three timepoints (anxiety) or two timepoints (activities; depression; somatic symptoms). Effect sizes were measured using Hedges' g to adjust for small sample size.
- 8.5 Responder Analyses: We conducted responder analyses using intent-to-treat principles with participants who dropped out classified as non-responders. Responder status was defined by SCID-5 anxiety diagnoses. To be classified as a responder, an individual would either no longer meet criteria for an anxiety diagnosis or would not meet full criteria for an anxiety disorder at post-treatment (i.e., *GAD* at baseline to *Anxiety Unspecified due to insufficient symptoms* at post-treatment).

9 Publication: The outcome of this trial have been published in the *American Journal of Geriatric Psychiatry*. <https://doi.org/10.1016/j.jagp.2018.12.018>

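### At week 8 the arms see different PMR videos between the resting and post-practice physiological readings, so an arm difference there cannot be put down to PMR experience alone

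*Combined protocol and SAP*

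**What the plan says.** Section 7.7 describes the week-8 visit in order. It opens with a resting measurement: "At post-treatment, a 5 minute baseline measurement of heart rate, blood pressure, and pulse will be obtained". Next, "the 16-muscle group PMR will be practiced by the BREATHE and the control group". The two arms do this differently. Controls proceed "by briefly viewing the initial PMR instructions video (control only) and then following along". For the other arm, "BREATHE participants will be shown the 16 muscle group practice video to follow along with". After the practice, "a 5-min physiological measurement period will be obtained to examine physiological variables as a function of participant's experience with PMR".

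Section 7.3 lists the physiological measures and places resting readings at baseline and post-treatment. On the reading after practice it says: "A five-minute post-relaxation practice will also be obtained at post-treatment". No reading after practice is planned at baseline.

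Section 7.5.1 describes the weekly lessons and adds: "Practice exercises are assigned each week and separate videos will be filmed to guide participants during practice". The instructions video and the practice video therefore appear to be separate items.

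Section 8.4 models anxiety, activities, depression and somatic symptoms. No part of section 8 names an analysis of the physiological variables.

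**The concern.** The second reading has a declared purpose, which is to relate physiology to experience with PMR. At week 8 that experience is represented by arm: BREATHE participants have been taught and have practised PMR, and controls have not been taught it in the trial. For arm to stand for experience, whatever happens between the two readings should be the same in both arms. Here the video shown also depends on arm.

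Randomization does not help, because the session difference comes after randomization and is assigned with the arm. At stake is how one comparison is read. A larger or smaller response in BREATHE could reflect weeks of practice, or it could reflect what each arm was shown in the minutes before the second reading. Nothing in 7.3, 7.7 or section 8 standardizes the session, records the interval or adjusts for the difference.

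**Working it through.** The plan gives no effect size, standard deviation (SD), power or session length for this comparison, so it has no figure to reproduce. The check is a comparison of the text by arm, followed by an illustration on stated assumptions.

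**1. The week-8 sequence by arm (section 7.7)**

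| Step | BREATHE | Wait list |
|---|---|---|
| First reading | 5 minutes, at rest | 5 minutes, at rest |
| Instructions video | not shown | viewed briefly |
| Guided practice | 16-muscle-group practice video | follows along; video not named |
| Type of PMR | 16 muscle groups | 16 muscle groups |
| Length of session | not given | not given |
| Second reading | 5 minutes | 5 minutes |

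**2. Two readings of the control row**

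- (a) Controls watch the instructions and then the same practice video. They have extra content and a longer interval.
- (b) Controls follow along with the instructions video itself. The guiding content differs, and the interval could be longer, equal or shorter.

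Content differs under both readings. A longer interval in controls follows only under (a).

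**3. What the contrast estimates**

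Let P be the mean change from rest over a PMR session in someone without experience, E the added effect of experience, and s_B and s_C the effects of the arm-specific session content and timing. On an additive scale:

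- BREATHE change = P + E + s_B
- Control change = P + s_C
- Difference = E + (s_B − s_C)

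The data give one contrast for two unknowns. The term (s_B − s_C) also enters if the second reading is compared directly between arms. It does not enter the comparison of week-8 resting readings, because those are taken before any video is shown.

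**4. Illustration only**

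Inputs from the documents: 40 randomized (section 7.2) in two equal groups (section 7.4), hence 40 / 2 = 20 per arm. Assumptions: two-sided alpha 0.05, a normal approximation, no true effect of experience (E = 0), and a session-driven shift of b SD.

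- Standard error of the difference = sqrt(2/20) = 0.316 SD.
- Probability of a false finding = Φ(b/0.316 − 1.96) + Φ(−b/0.316 − 1.96).
- Example, b = 0.50: 0.50/0.316 = 1.58, and Φ(−0.38) + Φ(−3.54) = 0.353.

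| Shift b (SD) | 20 per arm | 16 per arm (assumed losses) |
|---|---|---|
| 0 | 5.0% | 5.0% |
| 0.10 | 6.2% | 5.9% |
| 0.25 | 12.4% | 10.9% |
| 0.50 | 35.3% | 29.3% |
| 0.75 | 66.0% | 56.4% |

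The table shows how the risk would grow with b. The documents do not say which row applies, or in which direction the shift would run.

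**The case against.** The strongest reply is that the difference is deliberate and minor. Controls have not been taught PMR in the trial and need some instruction, the viewing is described as brief, and both arms practise the same type of PMR. The comparison is peripheral too: the GAS is the primary outcome (section 7.3), and section 8 does not list the physiological variables. Most of this stands, and it limits the weight of the point. It does not remove the point, because the need to instruct controls does not require the two arms to see different material between the readings.

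Four stronger inferences are tempting, and the documents do not support them.

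- *The interval is longer in controls.* No durations are given. Under reading (b) the control session could be as short as the BREATHE session, or shorter. Only the difference in content is established.
- *These readings are the only measure of the acute response to PMR.* Section 7.5.1 has BREATHE participants rate subjective distress (SUDS) before and after each practice. No such ratings are described for controls, so the most that can be said is that the week-8 readings are the only physiological measure around a practice, and the only one described for both arms.
- *The bias amounts to some number of mmHg.* Any such figure needs a session length, a drift in blood pressure and an SD, and the documents give none of them.
- *The trial's main result is affected.* The GAS is not part of this comparison. Section 7.7 lists the questionnaires after the practice, but their position in the visit is a different question from whether the two practice sessions match.

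It is also fair to say that 7.7 names no change score or test. The purpose statement does not fix the contrast, so the point is framed for both the post-practice reading and the change from rest.

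**Conclusion.** The point holds within a narrow scope. In section 7.7 the video content between the week-8 resting and post-practice readings differs by arm, and nothing else in the plan corrects for it. A between-arm difference in the post-practice reading, or in the change from rest, cannot be attributed to PMR experience alone. The interval may also differ, but this cannot be shown from the text.

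The size and direction are unknown, and a negligible effect is compatible with the documents. The percentages in the illustration depend on an assumed shift and on the other stated assumptions, and they are not estimates for this trial. The consequence is limited to the physiological practice comparison, which has no specified analysis. The week-8 resting comparison and the GAS stand outside it. This is a modest design correction and does not challenge the trial's main conclusion.

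**What to change.** For any further use of this protocol, amend 7.7 as follows.

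1. Keep the five-minute resting reading first in both arms, before any video.
2. Then show both arms the same session: the same brief instructions, followed by the same 16-muscle-group practice video.
3. Take the second five-minute reading, and record the interval between the two readings for each participant.

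This uses videos the plan already describes. The cost is a few minutes of repeated instruction for BREATHE participants and one extra timing field on the form. Recording the interval without matching the videos would not be enough, because content would still be aligned with arm.

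Do not solve the problem by moving the control-only video ahead of the resting reading. That would put an arm difference into the week-8 resting comparison, which is free of it as planned.

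Sections 8 and 9 show that the trial has been analysed and published. For data already collected, report the contrast as exploratory, state that the guided sessions differed by arm, and do not attribute a difference to PMR experience alone. This costs a sentence or two of reporting.

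### Participants who miss the week-8 visit are mailed only the GAS and PHQ-9, so they have no post-baseline SSS-8 or OASES, although the 8-item SSS-8 could go in the same envelope

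*Combined protocol and SAP*

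**What the plan says.** Section 7.6 makes week 8 an in-person assessment: "participants will come to the VA for a face-to-face post-treatment assessment". Section 7.7 places the SCID-5 anxiety sections, GAS, SSS-8, PHQ-9, OASES and ACS at that visit. For people who miss it, the one fallback named is partial data "through mailed questionnaires (GAS and PHQ-9) in participants who do not complete the final face-to-face assessment".

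Section 8.4 fits mixed models by maximum likelihood, with three timepoints for anxiety and two for activities, depression and somatic symptoms. For somatic symptoms the two are baseline and week 8. Section 7.3 describes the measure: "The SSS-8 is an 8-item somatic symptom assessment". The same section lists the 37-item OASES as a secondary outcome.

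On response, section 8.5 states "Responder status was defined by SCID-5 anxiety diagnoses" and has "participants who dropped out classified as non-responders". Section 8.2 treats drop-outs as those who did not complete the study, and adds only that efforts were made to get data from people who discontinued.

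**The concern.** A participant who misses the visit but answers the mail gives a week-8 GAS and PHQ-9 and nothing else. That person's only post-baseline SSS-8 and OASES values are lost, though they were willing to fill in forms. Maximum likelihood keeps them in the SSS-8 model on baseline data alone. The week-8 comparison then loses precision and leans more on the assumption that values are missing at random. No reason is given for leaving out the SSS-8. The ACS is different: it requires sorting 80 photographs, so its absence from a mailing is understandable.

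The responder analysis has a related gap. Only a SCID-5 can make someone a responder, and no route to one is described outside the visit. A participant who is reached by mail and is well seems to have no way of being counted as a responder.

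**Working it through.** The documents give no attendance rate, response rate or SSS-8 standard deviation, so there is no stated figure to reproduce. Every rate below is an assumption.

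**Inputs from the documents.** The goal is 40 randomized (7.2) in two equal groups (7.4), so about 20 per arm. Item counts are from 7.3: GAS 30, PHQ-9 9, SSS-8 8, OASES 37.

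**Packet length.**
- Now: 30 + 9 = 39 items.
- With the SSS-8: 39 + 8 = 47.
- With the OASES as well: 47 + 37 = 84, more than twice the present length.

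**SSS-8 precision.** Let n1 and n2 be the numbers with a week-8 value. The variance of the group difference is roughly proportional to 1/n1 + 1/n2. The standard deviation cancels from the ratio to the full-data case, 1/20 + 1/20 = 0.10. The small contribution of baseline-only participants is ignored.
- 16 vs 19 attend: (1/16 + 1/19)/0.10 = 1.15, so variance rises about 15%. The standard error rises by √1.15 = 1.07, about 7%.
- Half of the non-attenders recovered, 18 vs 19.5 on average: (1/18 + 1/19.5)/0.10 = 1.07, about 7% in variance.
- Equal loss with no recovery: 10% (18 per arm) gives 20/18 = 1.11; 20% (16 per arm) gives 20/16 = 1.25; 30% (14 per arm) gives 20/14 = 1.43. The standard errors rise by about 5%, 12% and 20%.

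**Responder analysis.** If p is the true response rate, m is the share missing the visit, and non-attendance is unrelated to response, the rate after imputing failure is p × (1 − m). Assume true rates of 50% (BREATHE) and 20% (wait list), a 30-point difference.

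| Missing, BREATHE vs wait list | BREATHE | Wait list | Difference |
|---|---|---|---|
| 20% vs 5% | 0.50 × 0.80 = 40% | 0.20 × 0.95 = 19% | 21 points |
| 10% vs 10% | 0.50 × 0.90 = 45% | 0.20 × 0.90 = 18% | 27 points |
| 5% vs 20% | 0.50 × 0.95 = 47.5% | 0.20 × 0.80 = 16% | 31.5 points |

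One true responder counted as a failure moves an arm's rate by 1/20 = 5 points. The difference can shrink or grow, depending on which arm loses more people.

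**The case against.** The best defence is that the plan protects what matters most. The GAS is taken by telephone at week 4 and mailed to those who miss week 8. A short packet is a sensible choice for people who are already hard to reach, since every added form could cost a primary-outcome return. That argument stands for the 37-item OASES, which is why adding it should be conditional. It has little force against 8 items on top of 39. Section 7.3 introduces the SSS-8 as characterizing somatic symptoms and does not label it secondary, but section 8.4 still models it as an outcome.

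A reader might go further and infer that the SCID-5 could simply be done by telephone. The documents do not show this. The telephone precedents are eligibility screening (age, a brief cognitive test, benzodiazepine use) and, at week 4, a rating scale: "participants will be asked to complete the GAS over the telephone". Both SCID-5 assessments are placed at in-person visits. The full interview takes 90 to 120 minutes. Week 8 needs less, "The Anxiety disorder sections of the SCID-5 will be administered at post treatment", but how much less is not stated.

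A reader might also infer that the plan explicitly scores mail-returners as failures. It does not: section 8.5 leaves dropping out undefined. The inference is strong, because 8.2 equates drop-outs with non-completers, 7.7 describes these people as lost to follow-up, and only a SCID-5 defines response. It remains an inference.

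Finally, section 8 is in the past tense and section 9 reports publication. A change to the mailing can help only a repeat or successor trial. A definition of drop-out still helps readers of this one.

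**Conclusion.** The point holds as a cheap improvement to data collection. It is neither a contradiction in the plan nor an error of analysis, and it does not touch the primary GAS comparison. Under the assumed attendance of 16 vs 19, the cost is about 15% in SSS-8 variance (7% in standard error), and recovering half of the non-attenders roughly halves it. The true size is unknown without an attendance rate.

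The responder point is secondary. It would be tempting to conclude that imputing failure dilutes the treatment effect. The documents do not support a direction. Twice-daily practice may discourage attendance in BREATHE, and the later offer of treatment may encourage it on the wait list, but no rates are given. The assumed scenarios run from 21 to 31.5 points around a true 30. Nor does the analysis merely measure attendance: in those scenarios 80% to 95% of each arm has an observed SCID-5.

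**What to change.** - In 7.7, add the SSS-8 to the mailed packet. Add the OASES only if the team judges that 37 more items will not threaten return of the GAS. Record whether each week-8 value came by mail or in person.
- In 8.5, define who counts as having dropped out. Use observed SCID-5 status wherever one exists, and impute non-response only where there is no week-8 SCID-5 by any route.
- Where staff judge it feasible, offer the SCID-5 anxiety sections by telephone to non-attenders, and flag the mode.

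The first change costs a slightly longer packet and a few values collected by mail. The second costs a sentence or two of text. The third costs staff time for a few interviews of unstated length, plus a mode difference in the diagnostic outcome, so it should stay optional.
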